deposition disease, GDD) harm or potential harm to the human body, the FDA banned some linear GBCAs (such as: gadolinium diamine, gadolinium meglumine) in July 2015) Is used for special populations (eGFR<30ml/min/1.73m², acute kidney injury), while the European Medicines Agency (EMA) banned some linear GBCA intravenous (such as: gadolinium diamine, Gadopentetate meglumine) is used for body enhancement. Because the stability of large ring GBCA is better than linear GBCA, FDA and EMA do not make special requirements. Gd-terol, gadobutrol and meglumine gadoterate are all macrocyclic GBCA. Gd-DOTA is the only ionic macrocyclic gadolinium contrast agent with the best stability (conditional stability constant, dissociation half-life and chelation Evaluation of parameters such as residues), the safety is better. At present, the GBCA approved by the China Food and Drug Administration (CFDA) includes gadopentetate meglumine, gadolinium diamine, gadolinium fuseamide, gadolinium benzamide, gadolinium disodium gadolinate, and gadolinium. Butrol, gadoterol and gadoterate meglumine. In this study, linear gadolinium and macrocyclic gadolinium were used in enhanced magnetic resonance examinations. Acute adverse reactions (1h) and delayed adverse reactions (1h-1W) in patients with mild to moderate renal insufficiency after contrast injection , The occurrence of late-onset adverse reactions (1W-3M). To explore the incidence of adverse reactions of linear gadolinium contrast agents represented by gadolinium bisamine and macrocyclic gadolinium contrast agents represented by gadolinium meglumine in patients with mild to moderate renal insufficiency. For patients with mild to moderate renal insufficiency when doing CE-MRI, make the best choice of gadolinium to reduce the incidence of adverse reactions in such patients during enhanced MRI.

IV. The characteristics and safety of the drug

(I) Characteristics of the drug

Generic name: Gadodiamide Injection

Product name: OMNISCAN

Sample specifications: 15ml: 4.305g (a sterile solution containing 287mg/ml gadodiamide)

Generic name: Gadoteric Acid Meglumine Salt Injection

Commodity name: Jia Di Xian

Sample specifications: 15ml: 5.654g (a sterile solution containing 377mg/ml gadoteric acid meglumine salt)

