1. People who are allergic to the components of this product should not be used. Patients with a history of allergic reactions or suspected allergic reactions to other gadolinium chelates should not use this product.
2. Contraindications related to magnetic resonance: patients with built-in pacemakers and patients with built-in vascular clips.

【Precautions】

This product is for intravenous injection only. If there is extravascular exudation, it may cause local intolerance reaction, then local treatment should be done.

[figure not shown]
This product is forbidden to be used for subarachnoid (or epidural) injection.

Routine preventive measures should be taken in the following situations: such as screening out patients with pacemakers, built-in vascular clamps, infusion pumps, neurostimulators, electronic cochleae, and patients with suspicious metal foreign bodies in their bodies, especially in the eyes.

VI. Overall design

(I) Design of the trial

This trial is a post-marketing, single-center, prospective, and safety interventional study. The trial process is as follows:

(II) Patient selection and withdrawal

1. Inclusion Criteria

- 1) Patients aged 18 to 80 years old who require gadolinium based CE-MRI;
- 2) Patients with renal function $30\text{ml/min}/1.73\text{m}^2 \leq \text{eGFR} < 90/\text{min}/1.73\text{m}^2$;
- 3) Patients who are able and willing to comply with the required inspection requirements.

2. Exclusion Criteria

- 1) Patient who experienced allergic reactions to previous gadolinium based contrast agents;
- 2) Patient who had used gadolinium based contrast agents within 3 months;
- 3) Patient with acute renal failure;
- 4) Patient who cannot comply with or cannot tolerate the necessary fluid replenishment procedures;
- 5) Patient with major mental illness, impaired consciousness or other diseases considered by

researchers to affect observation.

3. Early withdrawal and termination of patients

- 1) Any situation that the researcher thinks the patient needs to quit;
- 2) Any situation that the patient's guardian thinks it is necessary to withdraw from the CE-MRI.
- 3) After the patient withdraws, the relevant information is no longer tracked and recorded, but the reason for the withdrawal should be recorded in detail.

(III) Visit description

Visit 1: after signing the informed consent form for CE-MRI;

Visit 2: within 60 minutes after contrast injection;

Visit 3: within 3 months after contrast injection;

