This experiment uses an electronic CRF form for manual review and computer inspection; follow the guidelines for filling in the CRF for this test; if there is questionable data after manual review or computer inspection, a data questioning form will be sent to the clinical trial unit and the investigator will sign and confirm the value Correction, data questioning and correction form should be kept.

(II) Statistical Analysis

1. Statistical Analysis Plan

The statistical analysis plan is led by the statistician, assisted by the data administrator, sponsor and researcher, and formulated through consultation. After the trial plan is finalized, statisticians are selected; when about 50% of the enrollment is completed, the statistical analysis plan is started, and the statistical analysis plan is determined when the enrollment of the last case is completed; the statistical analysis plan can be performed before the database is finally locked modify.

2. Sample size

This study is a post-marketing safety observation study, with a design sample size of 600 cases.

3. Statistical analysis sets and statistical methods

Because this trial is a safety monitoring study, the analysis set includes all patients who have used the study drug and have undergone safety evaluation.

The statistical analysis was done using SAS 9.4. This study does not estimate missing data.

All statistical tests are at the 5% level of significance, and the two-sided test may be expressed with a 95% confidence interval.

Describe the basic information of the patient, and use the mean, median, standard deviation, and range for continuous variables for statistical description. Categorical variables (nominal variables/ordinal variables) are described by frequency and frequency.

Calculate the number of adverse events, serious adverse events, adverse reactions and serious adverse reactions, the incidence and its 95% confidence interval, and the 95% confidence interval is calculated using the exact probability method. They are described separately according to the severity of adverse events and whether they are related to drugs.

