Taking adverse reactions and adverse events as dependent variables, taking gender, age, concomitant diseases, gadolinium diamine, gadoteric acid meglumine exposure, combined medication and other factors as independent variables, using Logistic regression to analyze the occurrence of adverse reactions or adverse events. Significant influencing factors, and estimate the odds ratio and its 95% confidence interval. The variables entered into the model will be confirmed in the statistical plan before the data is locked.

X. Trial summary and results publication

After the drug clinical trial summary is completed, at least there should be a statistical analysis report and a clinical trial summary report; after consultation with the investigator, the trial protocol or the results of the analysis after the analysis can be published, and the disclosure of confidential data is strictly prohibited.

The statistical analysis report is completed within one month after the database is locked, and the clinical trial summary report is completed within one month after the statistical analysis report is completed.

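### The withdrawal rule ends safety follow-up even for patients already injected and even when the investigator decides the withdrawal, so later adverse events are avoidably and irrecoverably missed

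*Combined protocol and SAP*

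**What the plan says.** Section VI (II) 3 (early withdrawal) has two triggers and one consequence. The first trigger is the investigator's: "Any situation that the researcher thinks the patient needs to quit". The second is the guardian's and is worded as a judgement that "it is necessary to withdraw from the CE-MRI". The consequence is that "After the patient withdraws, the relevant information is no longer tracked and recorded", apart from the reason, which is to be documented in detail. The consequence is not limited to exits before injection, and section VIII lets patients leave whenever they choose.

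For an injected patient, the scheduled observation after the 60-minute visit consists of serology within 2 weeks (section VI (III), Visit 1 table, item 18) and telephone calls at 3, 6, 12 and 24 months (section II (II)). Section III names delayed reactions (1 hour to 1 week) and late-onset reactions (1 week to 3 months) as targets.

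Section VI (IV) 1 requires reactions to be reported and entered in the EDC within 24 hours or 15 days, counted from when the investigator is notified. It does not mention withdrawn patients.

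Section IX (II) 3 states that "the analysis set includes all patients who have used the study drug and have undergone safety evaluation", that missing data are not estimated, and that for incidence "the 95% confidence interval is calculated using the exact probability method". The model is described as "using Logistic regression to analyze the occurrence of adverse reactions or adverse events". No denominator per time window, person-time or censoring rule is given. Section IX (II) 1 leaves room for one: "the statistical analysis plan is determined when the enrollment of the last case is completed", with changes allowed until database lock.

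**The concern.** A rule that stops data collection at withdrawal is usually tied to stopping a treatment. Here there is one injection and nothing left to stop. For a patient already injected, the rule switches off only the safety follow-up on which the primary outcome depends, even when the investigator alone decided the withdrawal and the patient never declined contact.

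A first event after withdrawal is then seen only if someone happens to notify the investigator. Even in that case, one section says nothing further is recorded while another requires entry, and no order of precedence is given. The denominator can still be settled in the SAP, but follow-up that was never collected cannot be recovered.

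**Working it through.** **Does the rule reach injected patients?** The guardian item refers to leaving the scan and may have been meant for exits before it. The investigator item carries no such limit, section VIII allows exit at any time, and follow-up runs to 24 months. As written, the rule applies after injection.

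**Is there a backstop?** The section VI (IV) duties start at notification, so they create no active contact. The recorded reason may capture an event that prompts the withdrawal. Neither covers a first event that occurs later.

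**Direction.** Let p be the true risk of a first event after 60 minutes, w the share withdrawn, p_w the risk in those patients, and f the share of their first events that fall after withdrawal and go unreported. With all dosed patients as denominator:

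observed = p − w·p_w·f

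The lost term cannot be negative, so the bias is zero or downward. It is zero only if no first event is lost. Random withdrawal is not enough to make it zero.

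**Size.** The plan has no figure to reproduce: it gives 600 patients and no withdrawal rate or event timing. Everything below except the 600 is an assumption.

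- Risk R = 8.5% over 24 months, borrowed from the pooled gadoterate trials in section IV (II) (241/2822 = 8.54%, no follow-up period stated). This gives 600 × 0.085 = 51 patients with an event.
- All first events occur after the 60-minute visit. 20% of patients (120) withdraw, at times spread evenly over 24 months. No later event is notified.

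*Constant hazard, non-informative withdrawal.* h = −ln(0.915)/24 = 0.003701 per month. The average risk observed before withdrawal is 1 − 0.085/(24h) = 1 − 0.085/0.08883 = 4.31%. Observed incidence = 0.8 × 8.5% + 0.2 × 4.31% = 7.66%. Lost: 600 × (0.085 − 0.0766) ≈ 5.0 of 51, a relative bias of −9.9%. At 5/10/30% withdrawal the losses are 1.3/2.5/7.5.

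*Withdrawn patients at twice the hazard, overall risk still 8.5%.* Solving 0.8(1 − e^(−24h)) + 0.2(1 − e^(−48h)) = 0.085 gives risks of 7.17% (stayers) and 13.82% (withdrawn), of which 7.08% falls before withdrawal. Lost: 120 × (0.1382 − 0.0708) ≈ 8.1; observed 7.15%.

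*All events within 3 months, non-informative.* The average risk observed before withdrawal is (3 × 4.31% + 21 × 8.5%)/24 = 7.98%. Lost: 120 × (0.0850 − 0.0798) ≈ 0.6.

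*Everyone who withdraws leaves right after Visit 2.* Lost: 120 × 0.085 = 10.2, or 120 × 0.1382 = 16.6 at twice the hazard.

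*Lower base rate.* Section IV (II) also reports post-marketing adverse events below 1.0%. At 1% (6 patients), with constant hazard and non-informative withdrawal, about 0.6 are lost.

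**Other denominators (20% withdrawing evenly, true risk 8.5%).**

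| Hazard in withdrawn vs stayers | All dosed | Kaplan-Meier | Completers only |
|---|---|---|---|
| Twice | 7.15% | 7.89% | 7.17% |
| Half | 8.02% | 8.93% | 9.42% |

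The all-dosed figure is low in both rows. The other two can go either way, and censoring alone does not remove the bias.

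**Between agents.** With equal true risk, and withdrawal that is equal in amount, timing and relation to risk, the ratio is not distorted. Non-informative withdrawal of 10% versus 30% at constant hazard gives 8.08% versus 7.24%. The ratio is 0.90, and the gap of 0.84 points compares with a standard error of 2.17 at an assumed 300 per arm.

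**The case against.** The strongest reply is that the downward bias belongs to an analysis the plan has not clearly adopted. The stated set requires dosing and a safety evaluation, no rule per time window is given, and the SAP is still open. This stands: a reader might infer that the reported incidence will be too low, and the documents do not support that without the all-dosed condition.

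Second, capture is better than a bare reading of the rule suggests. The reason must be documented in detail, and notified reactions must be entered with no exception for withdrawn patients. This narrows the gap but does not replace the calls, and the conflict between the two sections remains.

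Third, the effect may be very small. For reaction windows ending at 3 months with evenly spread withdrawal, less than one patient is lost, and no withdrawal rate is given. This also stands. The illustrations are not ceilings, however: early withdrawal, or withdrawal linked to risk, loses more.

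Fourth, denominators per window and a time-to-event analysis are SAP choices that can still be made. Agreed; they are optional here. Continued follow-up is different because it cannot be added afterwards.

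**Conclusion.** The point holds and should be fixed. Its basis is that the rule discards safety follow-up the trial already plans to collect, for injected patients who may never have refused contact, and that this loss cannot be repaired later. It does not rest on a demonstrated size.

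Under the assumptions shown with 20% withdrawing evenly, the expected loss runs from about 0.6 to about 8 of 51 first events. It is nil if every event is acute and more if withdrawal is early or more strongly related to risk. The real figure cannot be determined from the documents.

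A reader might also infer that the comparison of the two agents is distorted. That would require withdrawal, or its link to risk, to differ by agent, and nothing in the documents indicates that it does. Nor do the documents say that the reporting duty lapses at withdrawal; they leave the matter unsettled.

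**What to change.** Replace the consequence in section VI (II) 3 with:

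> A patient who has received contrast continues the planned safety follow-up unless the patient refuses further contact. Investigator-decided withdrawal does not end adverse-event follow-up. Events notified after withdrawal are entered as in section VI (IV).

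Limit the present no-tracking rule to exits before injection and to patients who refuse contact. Record the withdrawal date and whether contact is refused, beside the reason.

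In the SAP, report post-injection withdrawals by agent, time and reason. A named denominator for each time window, and a time-to-first-event summary censored at last contact, are useful optional supplements. They do not replace continued follow-up.

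The cost is a protocol amendment with ethics approval (section VIII), consent wording that covers continued contact (the consent pages are not in the documents), and small form changes. The Visit 2–6 form as listed shows no last-contact date; the electronic form itself is not available to check. The calls are already planned, although withdrawn patients who have not refused would keep being called. Patients who refuse contact are lost either way.

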This trial is a prospective, interventional study. According to the requirements of the study, 600 cases of patients with mild to moderate renal insufficiency were enrolled. Gadodiamide and gadoteric acid meglumine salt were used for enhanced MRI. Observe the adverse reactions within 60 minutes of using the gadolinium contrast agents; follow up by telephone at 3, 6, 12, and 24 months after the inspection.

III. Background information of clinical trials

The principle of Magnetic Resonance Imaging (MRI) relies on the magnetic field generated by water molecules in the human body. It has high resolution in soft tissues (such as the nervous system, parenchymal organs, and muscle tissue), and uses non-ionizing electromagnetic radiation. Known exposure risk, many imaging parameters (sequence, proton density, T1 and T2 relaxation time) and many other advantages, since it entered the clinic in the 1980s, it has been clinically proven to be a valuable imaging diagnostic method. In the early clinical practice, MRI was mainly used for unenhanced magnetic resonance imaging, and the value of Contrast Enhanced-Magnetic Resonance Imaging (CE-MRI) in the diagnosis of diseases was not recognized. In the later stage, due to CE-MRI in small lesions, inflammation, edema and tumor Such diagnostic advantages have become an important supplement to MRI. At least about 30% of disease MRI diagnosis requires injection of magnetic resonance contrast agents.

In 2000, Cowper described the mucoedema-like sclerosis skin disease of renal dialysis patients in the Lancet magazine, that is, Nephrogenic Systemic Fibrosis (NSF). In 2006, Grobner

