Visit 4: within 6 months after contrast injection;

Visit 5: within 12 months after contrast injection;

Visit 6: within 24 months after contrast injection;

Visit content: study-CRF table-patient basic information table

Visit 1: study-CRF table-patient basic information table

1. Name of hospital:
2. Registration Date:
3. Contact details of the patient/its agent:
4. source: Outpatient () Hospitalized ();
5. Clinical department;
6. Name:
7. Sex: Male () Female ();
8. Age:
9. Weight: Kg;
10. Height: CM;
11. CE-MRI informed: yes () no ();
12. CE-MRI Indications:

13. Gadolinium contrast injection time:

14. Gadolinium contrast agent injection volume: ml;

15. Gadolinium contrast injection method: Push () Machine injection () (Please mark the injection speed);

16. Previous image enhancement examination history: time; Contrast agent name; Yes/No adverse events occurred;

a) yes time symptom severity;

17. Past history of adverse drug reactions: yes/no, yes time、AE symptom、severity;

18. The latest serological examination before CE-MRI and the serological examination within 2 weeks after CE-MRI;

19. History of allergy: yes/no, yes, allergy description;

20. Suspected existing disease:

21. Existing disease treatment plan: medical treatment () oral () Intramuscular injection () Intravenous injection () Surgical treatment () surgical intervention () Else;

22. History of illness:

a) Disease name Date of diagnosis duration;

23. Daily medication (Take medication within 1 week):

a) Generic name of the drug Taking method dose

24. Other information

25. Adverse event: yes () no ()

Visit 2, Visit 3, Visit 4, Visit 5 and Visit 6 Study-CRF Form-Contrast Adverse Events

1. Name:
2. Sex:
3. Age:
4. Weight:
5. Time to onset of adverse events:
6. Severity assessment:
7. Suspected drugs: Generic name (including dosage form)、Manufacturer、Production batch、Dosage、Start and end time of medication、Reason for medication;

8. Concomitant drugs: Generic name (including dosage form)、Manufacturer、Production batch、
Dosage、Start and end time of medication、Reason for medication

Concomitant drugs are those used within 24 hours;

9. Other suspected factors: Such as: patient disease progression, patient treatment plan, etc.;

10. Adverse events affect organ systems:

11. Adverse event name: refer to MedADR glossary;

12. Process description and handling of adverse events (attachment available);

13. Adverse event results:

Recover () Improve () Not getting better () Unclear ()

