Have adverse events () manifestation: _____

death () Direct cause of death: _____ Time of death: y m d

14. Impact on the original disease:

Not obvious () Prolonged course () Worsening () Cause adverse events () Cause death ()

15. Whether the withdrawal/reduction reaction is reduced or disappeared:

yes () no () unclear () No discontinuation or dose reduction ()

Whether the same reaction occurs again after re-use

yes () no () unclear () Unused ()

16. Relevance evaluation:

Certain () Very likely () Possible () May be irrelevant ()

Wait to be evaluated () Can't evaluate ()

17. Reporter's information: name, contact number, email address, occupation

(IV) Evaluation Standard

1. Adverse events

Adverse Event (AE) : Adverse clinical events that occur during the course of drug treatment may not necessarily have a causal relationship with the drug.

Serious Adverse Event (Serious Adverse Event, SAE): the reaction of one of the following

damages caused by the use of drugs:

- 1) Cause death;
- 2) Life threatening;
- 3) Carcinogenic, teratogenic, and birth defects;
- 4) Cause significant or permanent human disability or damage to organ function;
- 5) Lead to hospitalization or prolonged hospital stay;
- 6) Causes other important medical events, if not treated, the conditions listed above may occur.

Report serious adverse events:

- 1) When an aggregated, serious, or new (not listed in the ACR Contrast Media Guide) adverse reaction occurs, the investigator must within 24 hours of being notified:
- 2) Fill in the "Adverse Event/Reaction Report Form" and report to the Research Center Ethics Committee;
- 3) Entering adverse reaction events into EDC allows researchers to process relevant safety information/take corresponding measures immediately;
- 4) When a known mild to moderate adverse reaction occurs, the researcher needs to fill in the "Adverse Event/Reaction Report Form" within 15 days after being notified, and complete the entry of the adverse reaction event into the EDC to facilitate timely information about the adverse event;

2. Severity assessment

AE severity refers to the degree of occurrence of a specific event (which can be SAE or ordinary AE), but the event itself may have relatively small medical significance.

Principle of severity

Mild symptoms or signs that are easily tolerated

Moderate symptoms and signs cause discomfort and affect daily life;

Severe Cannot engage in daily life or work, need sick leave or necessary treatment.

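### The specified Visit 2–6 form does not require any record separating patients called and well from patients never reached, so incidence after 60 minutes can be understated

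*Combined protocol and SAP*

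**What the plan says.** Section II (II) plans observation for 60 minutes after injection and then "follow up by telephone at 3, 6, 12, and 24 months after the inspection". Section VI (III) numbers the 60-minute observation Visit 2 and the later contacts Visits 3 to 6.

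All five visits share one form, "Visit 2, Visit 3, Visit 4, Visit 5 and Visit 6 Study-CRF Form-Contrast Adverse Events". Items 1 to 4 are name, sex, age and weight. The form then goes directly to "5. Time to onset of adverse events", and items 5 to 16 describe an event and the suspected and concomitant drugs. Item 17 is the reporter's details. Item 13 gives the outcome of an event: "Recover () Improve () Not getting better () Unclear", then "Have adverse events () manifestation", then death.

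The Visit 1 form ends with item 25, "Adverse event: yes () no".

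On analysis, section IX (II) 3 states that "the analysis set includes all patients who have used the study drug and have undergone safety evaluation" and that "This study does not estimate missing data". It asks for incidence with exact 95% confidence intervals and gives no denominator for any follow-up period. Section VI (II) 3 requires a reason to be recorded when a patient withdraws. It does not mention patients who cannot be reached.

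**The concern.** The primary outcome is the incidence of adverse events. Section III divides adverse reactions into acute (first hour), delayed (one hour to one week) and late-onset (one week to three months). Scheduled adverse-event observation ends at 60 minutes, and the next scheduled contact is the 3-month call. Planned ascertainment of the second and third windows, and of everything up to 24 months, therefore depends on telephone calls.

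If the record does not show which calls succeeded, silence can be taken for absence of events. Follow-up incidence then comes out too low, the exact interval rests on more patients than were observed, and a result of no late cases looks more reassuring than it is. A statistical analysis plan written later cannot recover contact status that was never collected.

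**Working it through.** **Step 1: the form, item by item.** The 17 items of the Visit 2–6 form were checked for four things.

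| Needed to interpret a call | Where found |
|---|---|
| Visit number | No item |
| Date of contact or attempt | No item (item 5 concerns onset of an event) |
| Reached / not reached | No item |
| Any adverse event, yes/no | No item; the tick box in item 13 is an event outcome with no negative counterpart |

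Item 25 of the Visit 1 form is single and undated. It cannot show which of the four calls was made or what each one found.

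**Step 2: two patients side by side.** Both are injected and observed for 60 minutes without an event. At 3 months one answers and is well; the other never answers and has not withdrawn. No field in the protocol has to differ between them.

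**Step 3: the analysis set, read both ways.**
- Broad reading: the 60-minute observation counts as the safety evaluation. Both patients are in the set for all later incidence.
- Strict reading: a patient counts for a period only if evaluated in it. The second patient should drop out, but the form does not show who was evaluated.

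The gap remains on either reading.

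**Step 4: size, as illustration only.** The plan states no contact rate, late-event rate or allocation ratio, so it has no figure of its own to reproduce on this point. The sample size of 600 is not in dispute.

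Inputs:
- p = 8.5%: 241/2822, the all-event figure from the gadoterate meglumine trials in section IV (II).
- p = 1.0%: the upper bound quoted there for post-marketing studies.
- d, the share unreached: assumed 20%.
- 300 patients per agent: assumed from 600 in total.

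Formula: reported incidence = p × (1 − d). This assumes that the events concerned are found only by the calls, that non-contact is unrelated to having an event, and that unreached patients are counted as event-free.
- 0.085 × 0.80 = 0.068, or 6.8%
- 0.010 × 0.80 = 0.008, or 0.8%

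Interval at p = 8.5% and d = 20%: 600 × 0.068 = 40.8, taken as 41 events.
- 41/600: exact 95% limits 4.95% to 9.16%, width 4.21 points
- 41/480 (600 × 0.80 reached): 6.20% to 11.41%, width 5.21 points

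No cases observed: the two-sided exact 95% upper limit is 1 − 0.025^(1/n).
- n = 300: 1.22%
- n = 240 (300 × 0.80): 1.53%

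The zero-case comparison needs no event rate, only the share reached.

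**The case against.** The strongest reply is that the item list is not the finished case report form. Sections VII (I) 2 and IX (I) refer to a database developed from the protocol, an electronic form and filling guidelines, none of which is in the documents. A contact-status field may exist there. Nor does the protocol say that the form is left uncompleted for a well patient: identifiers filled in and event items left blank could mark a successful, negative call. Section VI (IV) separately names a report form for adverse events and reactions, and the documents do not say whether it is the same form. This stands against any claim that contact status is unknowable. It does not supply a requirement: the protocol lists form content item by item and states no convention for blank items.

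A reader might infer that the plan counts unreached patients as event-free. The documents do not say so. No follow-up denominator is written out, the analysis plan is still to be finalised, and the statement on missing data can be read as ruling out that kind of imputation.

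Item 25 may also stay open after injection, since the same form holds injection time and serology up to two weeks after the scan. It could record overall event status, but not status call by call.

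Finally, the 8.5% figure covers all events for one agent, including any that the 60-minute observation would catch. The shrinkage applies only to the part of incidence that depends on the calls. That is why 1.0% is shown beside it.

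**Conclusion.** The point holds as a gap in what the protocol requires. As specified, the form does not separate a negative call from no call, the analysis set is met at 60 minutes, and no follow-up denominator is defined. Incidence after 60 minutes can therefore be biased downward and its exact intervals too narrow. If unreached patients are kept as event-free, the call-dependent incidence shrinks by the factor (1 − share unreached), which is one fifth in relative terms at an assumed 20%. If illness or death causes non-contact, the understatement could be larger.

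Two stronger readings are not supported. One is that the gap creates a false difference between the agents. That needs unequal contact rates, and the documents give none; both agents share one centre and one call schedule. The other is that detection of nephrogenic systemic fibrosis is the reason for 24 months of calls. The documents do not state that purpose, and the skin examination and biopsy outcome is not something a telephone call captures.

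This is a cheap improvement, best made before calls begin because missed contact status may not be recoverable later.

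**What to change.** **Form, section VI (III).** At each of Visits 2 to 6, for every injected patient, record:
1. visit number;
2. date of contact or attempt;
3. status: reached, not reached, withdrawn or died;
4. any adverse event since last contact: yes or no.

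Complete the existing event items only if the fourth answer is yes.

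**Analysis, section IX (II) 3.** Estimate follow-up incidence with censoring at last successful contact. Alternatively, define a denominator for each window that keeps every patient with an event or death recorded before loss. Restricting the denominator to patients reached at or after the end of a window would not do. It would drop patients with a recorded event who are later lost, and section VI (III) sets the visits within 3, 6, 12 and 24 months, so a planned contact may come before the window closes. Report the number not reached by agent and visit.

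**Cost.** Four fields on an electronic form and a short addition to the analysis section; the calls are already planned. The downside is smaller numbers at risk in the late windows and wider intervals. Censoring also assumes that loss of contact is unrelated to events, and the reported numbers not reached help a reader judge how much rests on that assumption.
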